## 7.3.4 Safety Analysis

All subjects enrolled into the study, who receive study medication, are evaluable for safety. The frequencies of AEs by type, body system, severity, patient BMI, and relationship to study drug will be summarized. SAEs (if any) will be described in detail. AE incidence will be summarized by dose and placebo along with the corresponding exact binomial 95% two-sided confidence intervals.

## 7.4 Sample Size and Power

The primary analysis of the processing speed data is broadly based, reflecting the fact that that this is a feasibility study in which we have limited knowledge regarding the temporal patterns of decline and recovery in human neurocognitive functioning following concussion. We hypothesize that BCAA-treated groups will differ from placebo at specific time periods. The power calculation is based on comparisons of each dose group to placebo at each of the key time periods. These time periods each encompass three daily measurements per subject. With 10 subjects per dose group, and three repeated measurements per subject we have 80% power to detect mean differences in processing speeds between the BCAA group and the placebo group on the order of 0.122 seconds. Putting this in the context of a mean processing speed for healthy individuals of ages 14 to 34 of 2.46 to 2.51 seconds (Axon Sports unpublished), means that detectable differences between groups are on the order of 5% of the mean of a healthy individual. The analysis is based on a standard deviation in healthy individuals of 0.08, which we inflated to 0.10 based on our experience with injured or sick subjects, where variances are generally larger than their healthy counterparts. The intra-class correlation coefficient was set to 0.5. The calculation assumes a two-sided family-wise Type I error rate of 0.05 and uses a Bonferroni correction with four contrasts for each time period. The overall sample size is thus 50 subjects. We will consider a subject who contributes data up until and including at least Day 10 to be "evaluable for efficacy." We conservatively anticipate that no more than 72 subjects will be enrolled in order to achieve 50 evaluable subjects. We anticipate that it will take us approximately 12-18 months to recruit these subjects.

# 8 STUDY MEDICATION

## 8.1 Description

The three BCAA's, valine, isoleucine, and leucine, will be dissolved in water and combined with sodium gluconate, Tropical Punch Kool-Aid® powder, and sucralose to improve palatability.

## 8.1.1 Packaging

Study product will be packaged by the Investigational Drug Service (IDS) at the Hospital of the University of Pennsylvania (HUP) into 20 oz bottles containing 591 mL of blinded doses active drink (containing valine, isoleucine and leucine) or matching placebo (similar in appearance and taste but absent the three amino acids). Each bottle will be individually labeled and sealed with a tamper-evident cap, then packaged in corrugated cartons (with a carry handle) in sets of 14 (representing a one-week supply).

# 8.1.2 Labeling

Study product will carry labeling that clearly identifies the study, treatment code and directions, as well as the statement 'Caution: For Investigational Use Only'. Each label will identify the study day (Day 1, Day 2, etc.) and the labels will be color coded for MORNING dose (yellow) and EVENING dose (blue). A detailed label on the outside of the carton will identify the subject, date, prescriber, emergency phone number, study, federal caution statement (noted above) and detailed directions for use. A smaller removable label, will be placed on the carton and will be peeled off and pasted into the subject's study records at the time of dispense, as a clear record of which kit was issued to which subject.

## 8.1.3 Dosing

Four different doses of BCAA's will be used in this study, 15, 30, 45, and 54 grams per day (divided BID). Originally, 60 grams per day (divided BID) was used as the highest dose, however during the study precipitation issues were noted at the highest ratio due to leucine precipitating at a lower concentration than expected in to the presence of the other solutes. After further testing, it was determined that the product remained in solution at a concentration of 27g/591ml bottle and therefore, the highest dose level was altered to 54 grams per day. For each dose, the three BCAA's - valine, isoleucine and leucine - will be combined together in a 1:1:1 ratio and dissolved in 591 ml (20 ounces) of water (see table below). Additionally, 13 g sodium gluconate, 1.75 g unsweetened Tropical Punch Kool-Aid powder, and 9 g sucralose are added to the mixture to improve palatability. This mixture will be administered twice daily.

BCAA 27 g/bottle	BCAA 22.5 g/bottle	BCAA 15 g/bottle	BCAA 7.5 g/bottle
Valine 9 g	Valine 7.5 g	Valine 5 g	Valine 2.5 g
Leucine 9 g	Leucine 7.5 g	Leucine 5 g	Leucine 2.5 g
Isoleucine 9 g	Isoleucine 7.5 g	Isoleucine 5 g	Isoleucine 2.5 g
Sodium Gluconate 13 g			
Unsweetened flavoring	Unsweetened flavoring	Unsweetened flavoring	Unsweetened flavoring
1.75 g	1.75 g	1.75 g	1.75 g
Sucralose 9 g	Sucralose 9 g	Sucralose 9 g	Sucralose 9 g

04/06/2018 V 0.16

| QS to 591 mL |  |
|--------------|--------------|--------------|--------------|--|

23

The solution may be chilled or at room temperature, and should be shaken prior to consumption. The bottles may not be frozen or heated. Subjects are instructed to consume exactly 2 bottles in a 24-hour period. The recommended time between the two daily doses is 6 hours. The exact time given to consume a given bottle is not prescribed, although less than 60 minutes is recommended. If less than 2 bottles are consumed in a 24-hour period, the subject is instructed not to complete the remainder of the solution the following day and proceed to the bottles scheduled for that day. A study member is available 24 hours per day, 7 days per week by email and cell phone to answer dosing and other administrative questions.

The placebo solution will contain 1.2 g sucrose octaacetate (NF grade) and 30 g of microcrystalline cellulose (NF grade) dissolved in 591 ml of water. Additionally, 13 g sodium gluconate, 1.75 g unsweetened Tropical Punch Kool-Aid powder, and 9 g sucralose are added to the solution. This will ensure that the placebo solution has similar taste, texture, consistency and appearance as the BCAA solution.

BCAA's will be supplied by Spectrum Chemical and Laboratory Products. All ingredients in both BCAA and placebo solutions are USP/NF grade (see attached material).

### 8.1.4 Treatment Compliance and Adherence

Each day, subjects will self-report the number of bottles of the study medication that were consumed the prior day. Subjects will return all used, partially used, and unopened medication bottles at the conclusion of the study.

The study supplement will contain 500 mg/bottle of deuterium oxide that can be detected in the urine using isotope ratio mass spectrometry. Deuterium oxide has been used to assess drug compliance in both adult and pediatric research studies. Urine samples will be collected from all subjects for a baseline measure of deuterium oxide on Day 0 and then again on days 7 and 14 of the trial to assess adherence. These samples will be frozen and stored in the laboratory of [name]. Isotope ratio mass spectrometry will be conducted by the CHOP Metabolomics Core facility in a batched fashion at several points throughout the study. Deuterium oxide will be supplied by Cambridge Isotope Laboratories and is of suitable quality for use in human subjects (see attached material).

To assist with treatment compliance, subjects will be sent text, email or in-app alert messages twice a day to remind subjects to consume their study drink, and to reward them for compliance if they have documented consuming their drink.

## 8.1.5 Drug Accountability

Adequate records of study drug receipt and disposition will be maintained by the IDS Pharmacy at HUP. Records of receipts, investigational drug orders, dispensing records, and
disposition forms will be examined during the course of the study. The IDS at HUP will prepare treatment kits in advance of enrollment for rapid distribution when a subject enrolls.

The purpose of these records is to ensure regulatory authorities and the trial sponsor, the Dana Foundation, that the investigational new drug will not be distributed to any person who is not a study subject under the terms and conditions set forth in this protocol. The study medication is to be prescribed by the investigator or designee and may not be used for any purpose other than that described in this protocol. At study completion, all study products including partially used and empty containers will be destroyed on-site by the IDS Pharmacy and complete documentation will be maintained, with copies given to the investigator/sponsor.

## 9 SAFETY MANAGEMENT

### 9.1 Clinical Adverse Events

Clinical AE's will be monitored throughout the study.

The study coordinator will ask the subject about the occurrence of any AE's during the scheduled study visits conducted on days 7, 14, and 22 and during unscheduled visits. A standardized question will be asked of every subject to inquire about illnesses or accidents since the previous reporting period. The study coordinator will collect complete information about AE's from subjects including:

- Descriptive text and key words of the event
- Assessment of the event severity (grade)
- Indication if the event is serious and type
- Relationship to study drug
- Start date and end date (if applicable)

The investigators, with input from the independent medical monitor, will evaluate all AE's to determine the relationship to the study drug. All recorded AE's will be followed until resolution or stabilization. An AE Log will be used to collect this information across study visits and prompt follow-up of previously reported events.

Additionally, at the final study visit, subjects will be asked to call the study coordinator and report any serious AE's that they experience following the last visit, and that they believe may be related to their treatment.

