## 9.2 Adverse Event Reporting

The investigator is responsible for recording and reporting unanticipated problems related to research that occurs during and after study treatment. All on-site SAEs (CHOP or related sites) will be reported to the IRB in accordance with CHOP IRB policies. AE's that are not serious will be summarized in narrative or other format and submitted to the IRB at the time of continuing review. Since this is an FDA regulated study, [name] (IND Sponsor) will monitor AEs and report them to the FDA.

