## 9.3 Definition of an Adverse Event

An AE is any untoward medical occurrence in a subject who has received an intervention (drug, biologic, or other intervention). An AE is any unfavorable or unintended sign (including an abnormal laboratory finding, for example), symptom, or disease temporally associated with the use of a medicinal product, whether or not considered related to the medicinal product.

All AE's (including SAE's) will be noted in the study records and on the case report form with a full description including the nature, date and time of onset, determination of nonserious versus serious, intensity (mild, moderate, severe), duration, causality, and outcome of the event.

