#### **10.4 Regulatory and Ethical Considerations**

#### 10.4.1 Data and Safety Monitoring Plan

[name], an experienced neurologist, will act as the independent Medical Monitor for adverse events during this study. [name] has served in prior and ongoing clinical trials as endpoint adjudicator and was on the Clinical Event Committee for the pediatric EXCOR Berlin heart trial. She is presently a member of the endpoint adjudication committee for the Thrombolysis in Pediatric Stroke trial. The Medical Monitor will review all acute AE's regardless of how the investigator reports the relationship between the event and the study intervention. All patient deaths will be similarly reviewed. The study will also undergo monitoring by the CHOP Office of Research Compliance and Regulatory Affairs after each subject for the next six subjects enrolled and then at least annually throughout the duration of the study.

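### After the final visit, subjects are asked to report a serious adverse event on condition that they think it may be related, so they screen for causality before the investigators do

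*Combined protocol and SAP*

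**What the plan says.** Section 9.1 (Clinical Adverse Events) sets out two different ways of collecting events.

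- **Through the final visit.** The coordinator asks at each scheduled visit: "A standardized question will be asked of every subject to inquire about illnesses or accidents since the previous reporting period". The question carries no condition on cause. Judging cause is a later and separate step: "The investigators, with input from the independent medical monitor, will evaluate all AE's to determine the relationship to the study drug".
- **After the final visit.** The subject must take the initiative and phone in. The instruction given at Visit 4 is worded as follows: "report any serious AE's that they experience following the last visit, and that they believe may be related to their treatment". Two conditions are joined here. The event must be serious, and the subject must think that it may be related to treatment.

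The schedule of procedures (Table 1) places the last adverse event assessment on Days 22-24. The visit table in Section 5.2 puts Visit 4 in the same window. Section 4.1.2 gives 21 days of treatment. Sections 4.4.1 and 4.2 give an age range of 11 to 34 years and blinded, identical-looking kits.

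**The concern.** A subject who follows the instruction as worded has no reason to call about a hospital stay that he or she puts down to something else. Whether treatment contributed is the question that Section 9.1 otherwise gives to the investigators and the medical monitor. Subjects are poorly placed to answer it. They do not know their arm, and some are children. All have had a recent concussion, which offers a ready alternative explanation for a mood, cognitive or neurological event. Sections 2.4 and 10.4.2 name neurological and psychiatric effects as the theoretical risk of the product, so the events of most interest may be the ones a subject is least likely to link to a drink.

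Safety in concussed subjects is a stated secondary objective (Section 3.2). At stake is whether a late serious event reaches the people assigned to assess it.

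**Working it through.** The section contains no figure to reproduce. The check is a timing calculation, a comparison of the rules, and a search for another route.

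**1. When the change of rule takes effect.** Section 5.2 dispenses 42 bottles and Section 8.1.3 directs two per day, so 42 / 2 = 21 days, which agrees with Section 4.1.2. Taking Day 21 as the last treatment day and Days 22-24 as the last assessment, the gap is 22 - 21 = 1 day to 24 - 21 = 3 days. Collection without a condition on cause therefore stops about 1 to 3 days after treatment ends.

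**2. The two rules side by side.**

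| | Through Visit 4 | After Visit 4 |
|---|---|---|
| Who starts the contact | Coordinator, at scheduled visits | Subject, by phone |
| Which events | Any adverse event | Serious events |
| Condition on cause | None | Subject thinks it may be related |
| Who judges cause first | Investigators with the medical monitor | Subject; the investigators see what is called in |
| End of the period | Days 22-24 | Not stated |

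Narrowing to serious events after a short treatment is an ordinary choice. The condition on cause is the part that moves a judgement from the investigators to the subject. Section 9.4.1 grades each serious event on a scale that includes unlikely and unrelated, so the plan allows for serious events to come in without a presumption of cause.

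**3. Is there another route after Visit 4?**

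- Section 5.3 makes staff available for questions during the study.
- Section 5.7 has the coordinator contact early terminators, but only about returning bottles.
- Section 9.1 follows events that are already recorded until they resolve or stabilise.
- Section 9.2 sets reporting duties for events that become known. It gives no means of finding them.
- Section 9.5.1 covers follow-up of serious events already reported.
- Section 10.4.1 has the monitor review events that have reached the study.

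None of these is a scheduled contact or record check for a new event after the last visit. The subject's call is the only stated means.

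**4. Size.** The expected number lost is the number of serious events starting after Visit 4 multiplied by the probability that the subject does not call because he or she sees no link. The documents give neither factor, so no number follows. Few events are likely, since treatment is short and has already ended when the condition begins to apply.

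**The case against.** The other side has good arguments, and most of them limit the point.

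- **The threshold is low.** The wording asks about events that may be related, and it does not forbid other reports. A reader might infer that other late events will go unreported. The documents do not establish that. They show that such events are not asked for. Section 9.2 also keeps the investigator responsible for "recording and reporting unanticipated problems related to research that occurs during and after study treatment" and sends on-site serious events that become known to the IRB.
- **The request is an addition.** It follows complete questioning through Visit 4 and touches only events that start later. This stands, and it is why the effect is probably small.
- **There is no direct contradiction with Section 9.3 or 10.4.1.** It is tempting to set the sentence against the definition of an adverse event as one that counts "whether or not considered related to the medicinal product", and against the rule that "The Medical Monitor will review all acute AE's regardless of how the investigator reports the relationship between the event and the study intervention". That reading goes too far. The definition is tied to events that are temporally associated with use of the product and sets no collection period. The monitor is appointed for events during the study, and the rule concerns the investigator's opinion of cause, not what subjects are asked afterwards. The inconsistency lies within Section 9.1.
- **No harm to the comparison of arms is shown.** A reader might infer that the safety table by dose would rest on subjects' guesses. Section 7.3.4 does not say that events after the last visit enter that table. Because subjects are blinded, any under-reporting should act alike in all arms unless the blind fails.
- **Minors may not decide alone.** Parents consent for subjects under 18, and the documents do not say who would call. Consent pages are not available for review, so instructions given there cannot be judged absent.
- **Background risk looks low.** Section 2.4 states that no serious side effects of these amino acids have been reported. This supports a small expected number. It is not a reason to have subjects decide cause in a trial that lists safety as an objective.

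What remains is narrow: the only stated route for late serious events carries a condition on cause that the rest of Section 9.1 does not use.

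**Conclusion.** The point holds in a limited form. For serious adverse events that start after Visit 4, about 1 to 3 days after treatment ends, the plan's only stated means of learning of them is a call that subjects are asked to make if they believe the event may be related. Causality is thus screened by a blinded subject, or perhaps a parent, before the investigators and the medical monitor can judge it. This departs from the neutral questioning used up to that visit.

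The effect is probably small. It cannot be put into numbers, because the documents give neither a rate of late serious events nor a rate at which subjects would link them to treatment. No bias between arms is shown. The conclusion rests on two assumptions: that subjects act on the instruction as worded, and that no broader instruction is given in material outside the reviewed text. The change is worth making because it is cheap and removes a needless filter on safety reporting.

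**What to change.** In Section 9.1, delete the second condition of the sentence, the one on the subject's belief about relatedness, and make the same change in any script or handout used at Visit 4. Ask subjects, and the parents of minors, to report any serious event within a follow-up period that the sponsor specifies, whatever they think caused it. The investigators, with the medical monitor, then judge relatedness under Section 9.1, using the terms in Section 9.4.1.

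The same request could be added to the contact with early terminators in Section 5.7, which now mentions only the bottles.

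The cost is one sentence in the protocol, one line in the visit instruction, and the handling of a few unrelated reports. No dose, visit or analysis changes.

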## 9.2 Adverse Event Reporting

The investigator is responsible for recording and reporting unanticipated problems related to research that occurs during and after study treatment. All on-site SAEs (CHOP or related sites) will be reported to the IRB in accordance with CHOP IRB policies. AE's that are not serious will be summarized in narrative or other format and submitted to the IRB at the time of continuing review. Since this is an FDA regulated study, [name] (IND Sponsor) will monitor AEs and report them to the FDA.

## 9.3 Definition of an Adverse Event

An AE is any untoward medical occurrence in a subject who has received an intervention (drug, biologic, or other intervention). An AE is any unfavorable or unintended sign (including an abnormal laboratory finding, for example), symptom, or disease temporally associated with the use of a medicinal product, whether or not considered related to the medicinal product.

All AE's (including SAE's) will be noted in the study records and on the case report form with a full description including the nature, date and time of onset, determination of nonserious versus serious, intensity (mild, moderate, severe), duration, causality, and outcome of the event.

## 9.4 Definition of a Serious Adverse Event (SAE)

An SAE is any adverse drug experience occurring at any dose that results in any of the following outcomes:

- Death,
- A life-threatening event (at risk of death at the time of the event),
- Requires inpatient hospitalization or prolongation of existing hospitalization, or
- A persistent or significant disability/incapacity

Important medical events that may not result in death, be life-threatening, or require hospitalization may be considered an SAE when, based upon appropriate medical judgment, they may jeopardize the subject and may require medical or surgical intervention to prevent one of the outcomes listed in this definition.

A distinction should be drawn between serious and severe AE's. A severe AE is a major event of its type. A severe AE does not necessarily need to be considered serious. For example, nausea that persists for several hours may be considered severe nausea, but would not be an SAE. On the other hand, a stroke that results in only a limited degree of disability may be considered a mild stroke, but would be an SAE.

## 9.4.1 Relationship of Serious Adverse Events to Study Drug or Other Intervention

The relationship of each SAE to the study intervention will be characterized using one of the following terms: definitely, probably, possibly, unlikely, or unrelated.

